In **SSD adaptation**, scores on these CAT scales will determine whether participants move to a different level of care following their week 16 assessment: if participants who began in Tier I show mild to moderate depression or mild to severe anxiety without suicidality, they will be moved to Tier II, or if they show severe depression or suicidality, they will be moved to Tier III. Similarly, if participants who began in Tier II show severe depression or suicidality, they will be moved to Tier III. If a participant skips this assessment, the latest available CAT-MH scores are used.

In **DDD, triaging** will be determined by symptom scores from the CAT-MH in conjunction with variables from four overlapping, mutually reinforcing clusters. These clusters are: (1) social determinants of mental health, (2) early life adversity/stress, (3) predisposing, enabling and need influences upon health services use, (4) comprehensive mental health status. These clusters were selected based on available empirical evidence and theory. Statistical models that bridge the gap between traditional statistical models and machine learning models will be used for identify the minimum needed variables for these models. Data from prior STAND studies and implementations will inform the specific set of variables used for DDD during Year 1 of the present study. In subsequent years (Years 2-5), the algorithm will be updated and refined annually to optimize the predictive accuracy and utility of the decision-making tool.

The **DDD adaptation** algorithm will be put into practice in Year 2 of this study. During Year 1, all participants will receive SSD adaptation, while statistical models are used to develop DDD adaptation algorithm using the data from Year 1 of the present study, combined with data from prior STAND studies and implementations. In the DDD condition, participants in year 2 of the study are evaluated for treatment adaptation every 4 weeks. Participants in years 3-5 are evaluated for treatment adaptation every 8 weeks based on the output of the DDD adaptation algorithm, which will use data from the latest available CAT-MH scores and other relevant variables from the latest completed self-report measures.

Levels of Care

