Beginning July 8, 2025, participants in the ALACRITY Signature protocol that are initially assigned to Tier 2 or Tier 3 (in both SSD and DDD conditions) will additionally be randomized to one of two

conditions to examine the effect of a technology-enhanced suicide prevention intervention (TE-SPI) on suicide and self-harm risk. The two conditions will be:

- I. **Usual risk management (URM)** is the current standard of care in the project where participants receive outreach from ProtoCall Services and the study team after endorsing suicidal ideation in the weekly surveys.
- II. **URM + TE-SPI** adds a technology-enhanced suicide prevention intervention to the URM. The TE-SPI involves “caring contacts” messages sent to participants, and the use the eTUDES BRITE phone app, which provides users with a tailored coping plan, coping exercises to try in the moment, and a mood thermometer to log daily moods.

Aims

Specific Aim 1:

Triaging level of care - Evaluate whether data-driven algorithms for triaging to level of care lead to greater treatment adherence and outcomes than symptom severity triaging (Years 1-5). Hypothesis a: DDD will show greater adherence (session/lesson completion), greater improvements in depression and anxiety symptoms, and greater improvement in social, occupational and family functioning compared to SSD at 8 weeks. Hypothesis b: between-group differences will increase annually with refinements to DDD algorithms.

Analysis:

- Triaging Algorithm Development - The models we will explore bridge the gap between traditional statistical models and machine learning models which identify a subset of predictors that form a model that accurately predicts week 8 outcomes. This leads to approaches such as regularized regression models, including ridge regression, lasso regression, and elastic net regression that will allow us to identify a smaller and more manageable fixed set of baseline predictors that preserve the predictive accuracy enjoyed by the total set of predictors. At the end of each year, variables included in the predictive modeling will be reviewed for trimming or addition of new variables to be included.

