outcome) from baseline data, current tier and weeks 1-12 outcomes, we will use the model-based estimates for the fixed-effects (baseline and current tier), and the empirical Bayes estimates (see Hedeker and Gibbons, 2006189) for the random effects that describe the trajectory of the outcome based on the repeated assessments through 12 weeks. These fixed and random coefficient estimates will then be used to predict the distal endpoint (16 weeks) and based on this estimated outcome, treatment adaptation will be performed. Model selection will be based on minimizing the root mean square error (RMSE) between the actual observed 8-week outcomes and the estimated outcomes. Once calibrated, we will use this predictive model to set thresholds on what level of change or lack thereof will lead to adaptation of level of care (tier shift) at 4-week intervals of treatment rather than having to wait for several months to evaluate outcomes. The algorithm will be designed such that it will predict the lowest level of care that would produce improvement in symptoms at the outcome point.

Specific Aim 3:

Adapting Level of Care - Evaluate whether data-driven algorithms for adapting level of care lead to greater treatment adherence and outcomes than symptom severity adaptation (Years 2-5). Hypothesis a: Compared to SSD, DDD will show greater treatment adherence (session/lesson completion), greater improvements in depression and anxiety symptoms and social, family and academic functioning at 16 weeks, 24 weeks, 32 weeks, and 40 weeks. Hypothesis b: between-group differences will increase annually with refinements to DDD algorithms.

Analysis:

- Adaptation Outcomes: Outcome analyses will be conducted in three different ways similarly to the analyses planned for the triaging treatment outcomes. Secondary analyses will also be performed. These include 1) using a linear mixed model to explore mediating factors and 2) performing cost-effectiveness analyses of the adaptation algorithm.

Specific Aim 4:

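### The DDD review interval changes from 4 weeks (Year 2) to 8 weeks (Years 3-5), so Year 2 mixes adaptation into the Aim 1 triage contrast and confounds any Aim 3 annual trend that includes it

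*Protocol*

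**What the plan says.** The Condition Assignment section of the protocol sets three DDD adaptation regimes:

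- Year 1: "During Year 1, all participants will receive SSD adaptation", so the arms share one rule.
- Year 2: "participants in year 2 of the study are evaluated for treatment adaptation every 4 weeks".
- Years 3-5: "Participants in years 3-5 are evaluated for treatment adaptation every 8 weeks".

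For SSD, CAT scores "will determine whether participants move to a different level of care following their week 16 assessment". No earlier SSD review is scheduled. Under Levels of Care, anyone endorsing suicidality is offered clinical care at any time, in both arms and all years.

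Specific Aim 1 assesses triage at week 8 over Years 1-5. Specific Aim 3 assesses adaptation at weeks 16 to 40 over Years 2-5. Hypothesis b of both aims is that "between-group differences will increase annually with refinements to DDD algorithms". The analysis text of Specific Aim 2 has tier shifts triggered "at 4-week intervals of treatment rather than having to wait for several months" and mentions no 8-week review interval.

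**The concern.** Two attributions depend on the review schedule, and the schedule changes part-way.

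**Aim 1.** The week-8 contrast is presented as the effect of triage. In Years 1 and 3-5 no DDD algorithm review falls before week 8. In Year 2 one can fall at week 4, with no scheduled SSD counterpart. A participant moved then reaches the week-8 outcome partly in a tier chosen by adaptation. The adherence outcome is also affected, because a move changes which sessions or lessons are counted.

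**Aim 3, Hypothesis b.** Growth across years is credited to algorithm refinement. Between Years 2 and 3 the algorithm is updated and the interval doubles at the same time. Year 2 is an end point of the Years 2-5 range, so it has high leverage on any trend.

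At stake is what the results can be said to show: triage or triage plus adaptation, refinement or refinement plus a different review frequency.

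**Working it through.** **Do the planned analyses separate the two?** Under Aim 1 there are three: intent-to-treat, per-protocol and as-treated. The first includes Year 2 as it stands. The as-treated covariate flags only off-protocol shifts, and a scheduled week-4 DDD move is on-protocol, so it is coded 0. Nothing stated for the per-protocol set excludes such moves. Aim 3 uses the same three analyses. The protocol does not set Year 2 apart or adjust for the interval.

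**Inputs.** About 200 participants per year and 1,000 in total (Sample section); 100 per arm per year if allocation is 1:1; one-sided 5% test, 80% power and 5% dropout per assessment period (power statement under Specific Aim 4). Year is taken as enrolment-year cohort. Assumed: c is the extra Year 2 DDD-minus-SSD difference, in SD, due to the 4-week interval. The documents give no value for c, and it need not be the same at week 8 as at later visits.

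**Share of Year 2.** Aim 1: 200/1,000 = 20%. Aim 3: 200/800 = 25%.

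**Aim 1 pooled week-8 difference.** Shift = 0.20c. With c = 0.1 this is 0.02 SD; with c = 0.2, 0.04 SD. The detectable difference is (1.645 + 0.842) × √(2/n per arm):

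- All years, 500 × 0.95 = 475 per arm: 2.486 × √(2/475) = 0.16 SD.
- Without Year 2, 400 × 0.95 = 380 per arm: 2.486 × √(2/380) = 0.18 SD.

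**Annual trends.** The protocol states no model for Hypothesis b, so a least-squares slope over yearly differences is assumed. Each yearly difference has SE √(2/100) = 0.141 SD, ignoring dropout. Slope SE = 0.141/√SS, where SS is the sum of squared centred years. The weight of Year 2 is its centred value divided by SS. Detectable slope = 2.486 × SE.

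| Years used | SS | Slope SE (SD/year) | Detectable slope (SD/year) | Shift in slope per year |
|---|---|---|---|---|
| 1-5 (Aim 1) | 10 | 0.045 | 0.11 | (2 - 3)/10 = -0.10c |
| 1, 3, 4, 5 | 8.75 | 0.048 | 0.12 | 0 |
| 2-5 (Aim 3) | 5 | 0.063 | 0.16 | (2 - 3.5)/5 = -0.30c |
| 3-5 | 2 | 0.100 | 0.25 | 0 |

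**Range for Aim 3.** For c from -0.2 to +0.3 SD (assumed), the Years 2-5 slope shifts by +0.06 to -0.09 SD/year. As an illustration, a true slope of +0.05 SD/year would appear as 0.05 - 0.30 × 0.2 = -0.01 if c = +0.2, and as 0.05 + 0.06 = +0.11 if c = -0.2.

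**Would dropping Year 2 improve the Aim 3 slope?** Mean squared error is 0.004 + (0.3c)² with Year 2 and 0.010 without. Dropping it is better only if 0.3|c| > √0.006 = 0.077, that is |c| above about 0.26 SD.

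**The case against.** The strongest reply is that the effect is small and the remedy is analytic detail that a statistical analysis plan may hold. Much of this stands. With c = 0.1 the Aim 1 shift is 0.02 SD against a detectable 0.16 SD. The Aim 3 slope shift of 0.03 SD/year is about half its SE. Only participants actually moved are affected, with about four weeks for a week-4 move to act by week 8. The yearly shares are nominal, since the protocol says approximately 200 and its revision history records removal of the annual cap. The reply does not remove the point: the protocol itself fixes the schedules, the year ranges and the causal wording of Hypothesis b, and these do not fit together.

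A reader might infer more than the documents support:

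- *That no annual trend can be credited to refinement.* Years 3-5 share one interval, so a trend within them is not confounded by interval, only less precise.
- *That the SSD-DDD comparison is invalid.* Within each year it remains a randomised comparison of whole strategies. Only the attribution to triage or to refinement is affected.
- *That Aim 2 speaks only of 4-week periods.* It also calibrates on week-8 outcomes and predicts a week-16 outcome. The mismatch is confined to the interval for tier shifts.
- *That the Year 2 week-4 score could stand in for week 8.* This changes the endpoint for one year. If the effect grows linearly from zero, week 4 shows half the week-8 difference. For an effect of 0.26 SD (the size in the power statement, used only as an illustration) that is an error of 0.13 SD, larger than a c of 0.1.

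**Conclusion.** The point holds in limited form. As written, the Year 2 week-8 contrast combines triage with early adaptation, provided the first review is at week 4. Any annual trend that includes Year 2 combines refinement with a change of review interval. The size is about 0.20c on the pooled Aim 1 difference, -0.10c per year on an Aim 1 trend and -0.30c per year on an Aim 3 trend, under the assumed slope model and equal yearly accrual. The direction is unknown: if more frequent review helps, Year 2 is raised and growth is understated; if it harms, growth is overstated. The bias therefore cannot be called conservative. It is a problem of attribution and a cheap improvement, not a threat to the randomised comparison.

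**What to change.** 1. Keep the all-years analyses as main for both aims. Making Years 3-5 the main Aim 3 trend is not clearly better, given the precision lost.
2. Pre-specify a supporting Aim 1 analysis that omits Year 2. Cost: detectable difference about 0.18 instead of 0.16 SD.
3. Pre-specify a supporting Aim 3 trend on Years 3-5. Cost: detectable slope about 0.25 instead of 0.16 SD/year, so a null result there will say little. A separate Year 2 term gives the same slope estimate and gains no precision.
4. Wherever Year 2 is included, word the Hypothesis b conclusion as a change in the whole DDD package (algorithm plus review interval), and the Aim 1 Year 2 contrast as triage plus any early adaptation.
5. State when the first Year 2 review took place, and reconcile the interval in the Aim 2 analysis text with Condition Assignment. Which interval is right is not judged here.

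The protocol version is dated 01/26/2026 and places Year 4-5 from September 2025, so Year 2 has passed. The change is wording and two supporting models, with no change to conduct.

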- We will statistically compare the symptom outcomes (depression, anxiety) at 8 weeks between the SSD and DDD adaptation arms using linear regression models. The same general strategy will be used for functioning outcomes. In terms of treatment adherence, we will use generalized linear models (Poisson and negative-binomial regression models) that are appropriate for count outcomes such as number of sessions completed. Outcome analyses will be conducted in three different ways. (1) Our primary analysis will be an intent-to-treat (ITT) analysis. (2) Our second set of analyses is a “per protocol” (PP) analysis. (3) Finally, our “as-treated” (AT) analysis will include all data, but a covariate will be added describing any off-protocol shift in treatment (yes=1; else=0).
- Note that for Aim 1, outcomes will be assessed weekly through week 8. Therefore, the power analysis is essentially identical.

Specific Aim 2:

Adaptation Algorithm Development - Develop a predictive algorithm (Year 1) that combines individual baseline characteristics with time-varying symptom response, perceived support, and life stressors, during discrete 4-week periods to predict depression and anxiety symptom outcomes 4 weeks later. Over Years 2-5, algorithm generation and testing will be iteratively refined, and tested for racial/ethnic and other modifiers.

Analysis:

- We will use linear mixed-effects regression models with weekly assessments at baseline through week 8 to initially calibrate the predictive algorithm, separately for the depression and anxiety outcomes. To predict a future outcome (e.g. 16-week

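### The adaptation model is selected on week-8 error, while its forecasts for later weeks, for which no criterion is stated, drive the tier shifts

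*Protocol*

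**What the plan says.** The Analysis paragraph of Specific Aim 2 in the protocol takes three steps.

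- Calibration: "We will use linear mixed-effects regression models with weekly assessments at baseline through week 8 to initially calibrate the predictive algorithm".
- Use: fixed effects (baseline and current tier) and empirical Bayes random effects, in the example from weeks 1 to 12, "will then be used to predict the distal endpoint (16 weeks) and based on this estimated outcome, treatment adaptation will be performed".
- Selection, in the next sentence: "Model selection will be based on minimizing the root mean square error (RMSE) between the actual observed 8-week outcomes and the estimated outcomes".

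The fitted model then sets the thresholds of change that "will lead to adaptation of level of care (tier shift) at 4-week intervals of treatment". The statement of Aim 2 gives the forecast horizon: the algorithm is "to predict depression and anxiety symptom outcomes 4 weeks later".

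Condition Assignment has DDD reviews every 4 weeks in Year 2. After that, "Participants in years 3-5 are evaluated for treatment adaptation every 8 weeks based on the output of the DDD adaptation algorithm". Participation lasts 40 weeks. Aim 2 also says that the algorithm is refined iteratively in Years 2-5, but it names no other selection target.

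**The concern.** The model is chosen by its error at the last week of its own initial calibration window, and then relied on for weeks outside that window. A time shape that fits well up to week 8 can extrapolate badly, for instance a straight line through scores that are levelling off.

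The chosen model sets the tier-shift thresholds, so it is part of the experimental intervention. A poor choice could make DDD weaker than it need be. A null Aim 3 result would then be harder to read: the fault might lie with data-driven adaptation or only with the forecasting model.

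A smaller matter in the same text is that the 4-week tier-shift interval and 4-week horizon in Aim 2 carry no year limit, while Condition Assignment has 8-week reviews in Years 3-5.

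**Working it through.** The protocol gives no figure for this point. The 0.26 SD power statement is not an input, so there is nothing to reproduce first.

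**1. Which decisions does the criterion score?** A decision at week *d* with horizon *h* targets week *d + h*. A week-8 criterion scores it only if *d + h* = 8 and the prediction uses data up to week *d* only.

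- *h* = 4 (Aim 2): *d* = 4, the earliest possible review.
- *h* = 8: *d* = 0, which is triage, not adaptation.
- If the week-8 estimate uses week-8 data (in-window fit), no decision is scored.
- If *d* ≥ 8, then *d + h* ≥ 12, so the decision is never scored. This covers every review in Years 3-5 if reviews are counted from baseline.

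**2. Sensitivity to the schedule.** No decision weeks are listed, so any count rests on assumptions (reviews counted from baseline, *h* = 4).

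| Reviews assumed | Year 2 scored | Years 3-5 scored |
|---|---|---|
| Through 40 weeks, none at week 40 | 1 of 9 | 0 of 4 |
| Week 40 included | 1 of 10 | 0 of 5 |
| Ending before week 16 | 1 of 3 | 0 of 1 |

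The denominators move; the numerators do not.

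**3. Can the week-8 ranking mislead?** One assumed data set: 4,000 students, scores levelling off with time constant 6 weeks, residual SD 6, models fitted on weeks 0-8. RMSE:

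| Model | Week 8, fitted | Week 8 from weeks 0-4 | Week 16 from weeks 0-12 |
|---|---|---|---|
| Linear | 5.31 | 7.57 | 9.13 |
| Log-time | 5.58 | 7.49 | 6.48 |
| Quadratic | 5.50 | 7.44 | 9.47 |

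In-window fit picks the linear model, and the loss at week 16 is 9.13 − 6.48 = 2.65. Between linear and log-time, the forecast reading picks log-time and loses nothing. With the quadratic admitted, it picks that by 7.49 − 7.44 = 0.05 and loses 9.47 − 6.48 = 2.99. The week-8 forecast barely separates the candidates, and the loss depends heavily on which are tried.

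**4. Size over several trajectories.** Assumptions:

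- 20 runs, 200 training and 4,000 new students.
- Baseline mean 65, SD 12; residual SD 7, autocorrelation 0.3.
- Either levelling-off (mean drop 15, SD 10; time constant 3, 5, 8 or 15 weeks) or linear change (−0.5 per week, SD 0.7).
- Candidates: random intercept with fixed linear time, random linear slope, random log-time slope.

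RMSE at week 16 from weeks 0-12:

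| Selection rule | 3 | 5 | 8 | 15 | linear |
|---|---|---|---|---|---|
| In-window week 8 | 12.2 | 11.4 | 10.1 | 9.2 | 9.2 |
| Week 8 from weeks 0-4, held out | 8.8 | 9.0 | 9.4 | 8.7 | 10.2 |
| Held out, 4 weeks ahead, calibrated on weeks 0-16 | 8.3 | 8.0 | 8.0 | 8.2 | 9.0 |

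Row 1 minus row 3 is 3.9 / 3.4 / 2.1 / 1.0 / 0.2. Row 2 minus row 3 is 0.5 / 1.0 / 1.4 / 0.5 / 1.2 (largest 1.3 before rounding).

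Repeating the set-up reproduced the in-window figures closely. The forecast reading was less stable: about 0.1 to 1.3 in one repeat, and 0.0 to 1.9 in one of only 10 runs. Without the random-intercept-only candidate, its loss was at most about 0.7 in one repeat and 0.9 in another. Holding calibration at weeks 0-8 as well, so that only the selection sentence differs, leaves about 0.0 / 0.3 / 0.8 / 0.2 / 0.2.

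Row 3 was selected on decisions at weeks 4, 8 and 12, and week 16 from week 12 is one of its own targets. The table therefore speaks for that decision, not for later weeks.

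**The case against.** **The forecast reading is the fairer one.** The paragraph uses the word estimated for a forecast, and Aim 2 speaks of outcomes 4 weeks later. This stands. The losses near 4 belong to the in-window reading only and should not be taken as the main result.

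**8-week may not mean week 8.** The compensation section uses the term for the recurring assessments, and it could also be a slip for 16-week. The adjacent 16-week outcome favours week 8. On either alternative, the sentence still has to be corrected before it can be followed.

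**Calibration is only initial, and the algorithm is refined.** True, but no later target replaces week 8.

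**The simulation is not this trial's model.** Its candidates differ only in time shape and omit the baseline predictors, tier, support and stressors that Aim 2 names. This stands: the figures show what can happen, not what will.

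**Stronger readings that the documents do not support.**

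- A reader might infer a fixed count, such as one of nine Year 2 decisions. The review weeks are not listed, and average intervention length is put below 13 weeks, so the count is conditional.
- A reader might infer that later outcomes are modelled with tier shifts ignored. Current tier is already a predictor.
- A reader might take Algorithm v8, in the revision history, to be the adaptation model. The entry does not say whether it is triage or adaptation.

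**Conclusion.** The point holds in a limited form. The only stated selection criterion is week-8 error. It tests the earliest adaptation decision at most, and no forecast made at week 8 or later.

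The practical loss is unknown. With the assumed trajectories and three candidates, it is about 0 to 1.3 RMSE points on the 0-100 CAT scale under the forecast reading and up to about 4 under the in-window reading. It may be near zero. These are illustrations, not bounds: the quadratic candidate in step 3 of the working gives a larger loss.

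A reader might infer that the trial's comparison is compromised. It is not: a poorly chosen forecasting model leaves the validity and type I error of SSD versus DDD untouched. At worst, it weakens the experimental arm and blurs a null result. The severity is low to moderate; this is a cheap improvement.

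**What to change.** For any remaining update of the adaptation algorithm, replace the selection sentence with:

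> Models are selected by RMSE in held-out students at the forecast horizon in use, predicting only from data available at each decision point and averaged over the decision points in use, with calibration data spanning the predicted weeks.

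Keep current tier as a predictor, and let it vary with time when later weeks are scored. For adaptation versions already deployed, report forecast error at the weeks used for decisions.

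Separately, reconcile the 4-week tier-shift interval and the 4-week horizon in Aim 2 with the 8-week reviews for Years 3-5 in Condition Assignment. No interval is proposed here.

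The cost is a reworded sentence and a little extra computing, since CAT-MH is already collected weekly (Assessments). The reach is limited: the protocol is dated January 2026 and places September 2025 onward in Years 4-5, so only later updates can benefit.

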Title: STAND ALACRITY CENTER Signature Project: STAND Triaging and Adapting to Level of Care

Lay title: STAND Finding and adapting the level of care

Research study IRB# 22-000635

[figure not shown]
Protocol version: 01/26/2026

Research Description

The STAND ALACRITY CENTER Signature Project: STAND Triaging and Adapting to Level of Care study is a randomized controlled trial comparing 2 approaches for treatment triaging and adaptation. This study is being conducted among community college students enrolled in the Screening and Treatment for Anxiety and Depression (STAND) initiative at East Los Angeles College (ELAC). 1,000 students who meet study eligibility criteria will be enrolled over 5 years. Participants will be randomized to receive care under 1 of 2 models: symptom severity-based decision making (SSD) or data-driven decision making (DDD). Participation involves completing online self-report assessments in addition to engaging in an assigned depression or anxiety service as provided by this study. See **Figure 1** for general overview of the research design.

This study is funded by the National Institute of Health – National Institute of Mental Health. This research study is conducted by [name], from the Departments of Psychology and Psychiatry, and [name], from the Department of Psychiatry, at UCLA. This study is affiliated with the UCLA Depression Grand Challenge.

Figure 1

Sample

This study aims to enroll approximately 200 participants per year, for a total sample size of 1,000 participants over five years. To reach this sample size, we expect to consent up to 5,000 students.

Eligibility

Interested individuals are directed to the study webpage to learn about STAND at ELAC, and create an online account. Initial study eligibility is assessed through self-report questions administered during the account creation process. All individuals are informed during screening that they are welcome to sign up for the free virtual wellness program Stand For All, without participating in this research study. If an individual is deemed ineligible at any point during screening, they are notified and offered alternative resources, including Stand For All.

Inclusion criteria:

- Age 18 – 40 years
- Competent to understand informed consent and express willingness to follow study procedures.
- Currently enrolled ELAC student
- Either uninsured or on California Medicaid (Medi-Cal).
- Proficient in English
- Have private access to internet

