Study participation is completely remote and lasts 40 weeks after initial orientation/intake. Participation requires creating an online account on the STAND at ELAC study website in order

to complete eligibility screening. Once initial eligibility is confirmed, those who choose to participate must sign an online consent form and complete baseline assessments. Upon completion of baseline assessments, participants are randomized to 1 of 2 treatment conditions (SSD or DDD), and assigned to a level of care based on their responses to baseline surveys. Participants must attend a remote orientation or intake session for their assigned level of care, and thereafter are asked to complete weekly online surveys over the course of 40 weeks. Participants are considered enrolled after completing consent, baseline assessments, and attending an orientation/intake session for their assigned level of care.

Condition Assignment

Participants in this study will be randomized into one of two conditions which are differentiated by approach for decision making in treatment triage and treatment adaptation. The standard approach used in previous STAND studies is **symptom severity-based decision making (SSD)**. SSD participants will be triaged and adapted to level of care based on reported symptom severity only.

The experimental approach is **data-driven decision making (DDD)**. DDD participants will be triaged and adapted to a level of care using a multivariate predictive algorithm that is iteratively updated annually. This algorithm determines level of care based on individual participant characteristics, coupled with reported symptom severity. The DDD *triaging* algorithm will be implemented beginning in Year 1 of this project and the DDD *adaptation* algorithm will be implemented beginning in Year 2.

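### Aim 3 credits the SSD v DDD contrast at weeks 16-40 to adaptation alone, but one randomisation sets triage and adaptation together, so only the combined strategy is estimated

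*Protocol*

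**What the plan says.** The Research Description presents the trial as "comparing 2 approaches for treatment triaging and adaptation". The Condition Assignment section says the two randomised conditions are "differentiated by approach for decision making in treatment triage and treatment adaptation": SSD participants are both triaged and adapted on symptom severity, and DDD participants are both triaged and adapted by algorithm. No second randomisation at the adaptation stage is described.

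The adaptation rules also differ in timing:
- SSD: "scores on these CAT scales will determine whether participants move to a different level of care following their week 16 assessment". This is the only scheduled SSD adaptation.
- DDD, Year 1: "During Year 1, all participants will receive SSD adaptation".
- DDD, Year 2: "In the DDD condition, participants in year 2 of the study are evaluated for treatment adaptation every 4 weeks".
- DDD, later years: "Participants in years 3-5 are evaluated for treatment adaptation every 8 weeks".

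In both arms, suicidality leads to an offer of clinical care at any time (Levels of Care).

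Specific Aim 1 is the triage question, assessed at week 8. Specific Aim 3 is set up as a separate question about adaptation: "Evaluate whether data-driven algorithms for adapting level of care lead to greater treatment adherence and outcomes than symptom severity adaptation (Years 2-5". Its Hypothesis a compares DDD with SSD at weeks 16, 24, 32 and 40. Its analysis follows the same three approaches as the triage outcomes, and a secondary cost-effectiveness analysis is attached to the adaptation algorithm.

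**The concern.** Two components are assigned together, and the aim names only one of them. From week 16 onwards the arms differ in how participants were first placed, in the rule that moves them, and in how often that rule is applied. The arm difference carries all three. Read literally, a positive Aim 3 would be reported as evidence for data-driven adaptation, although a triage benefit lasting beyond week 8 could produce it alone. The possibility is not remote on the protocol's own terms, because Hypothesis 1a predicts a DDD benefit at week 8.

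Week 16 adds a question of interpretation. It is listed as an Aim 3 outcome, yet no scheduled SSD adaptation has happened by then.

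**Working it through.** **1. What is randomised.** Write the expected arm difference at an Aim 3 visit as D = T + A, where T is what remains of the triage effect and A is the effect of the adaptation rule, including its frequency and any dependence on the starting tier. To separate A from T, some Years 2-5 participants would have to be randomised to DDD triage with SSD adaptation, or the reverse. The protocol describes none. Only D is identified, whatever model is fitted.

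Year 1 pairs DDD triage with SSD adaptation, but it lies outside Aim 3. A Year 1 v Years 2-5 comparison would not be randomised, and it would be mixed with algorithm changes, since "the algorithm will be updated and refined annually to optimize the predictive accuracy".

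**2. Scheduled adaptation decisions before each outcome.** Assumptions: intervals run from baseline, enrolment year fixes the frequency throughout, and only decisions strictly before the visit count.

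| Outcome week | SSD | DDD, Year 2 | DDD, Years 3-5 |
|---|---|---|---|
| 16 | 0 | 3 (weeks 4, 8, 12) | 1 (week 8) |
| 24 | 1 | 5 | 2 |
| 32 | 1 | 7 | 3 |
| 40 | 1 | 9 | 4 |

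**3. The plan's own figure.** The power statement (printed just before Specific Aim 5) gives 0.26 SD at the last visit for 500 per arm, one-sided 5%, 80% power, rho 0.3 and 5% dropout between assessments. A linear group-by-time contrast over the four visits gives about 0.23 on those inputs. It gives 0.25-0.26 if the test is two-sided, or if it is one-sided with 800 participants in total. The contrast is not stated, so the figure can be neither confirmed nor faulted, and this point does not depend on it.

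**4. Illustration of the consequence.** Set A = 0 and let T be an assumed constant carry-over; the documents give no value. Years 2-5 at about 200 per year, split 1:1, give 4 × 200 / 2 = 400 per arm.

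Single visit, unit SD, one-sided 5%: P = Φ(T / √(2/n) − 1.645).
- Week 16, n = 400: √(2/400) = 0.0707. T = 0.10 gives Φ(1.414 − 1.645) = 0.41.
- Week 40, n = 400 × 0.95³ = 343: √(2/343) = 0.0764. T = 0.10 gives Φ(1.310 − 1.645) = 0.37.
- Week 40 with dropout also before week 16, n = 400 × 0.95⁵ = 309.5.

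Four visits together: AR(1) with rho 0.3, monotone 5% dropout between visits, 400 per arm at week 16. The SE of the average difference is 0.0455. The SE of the slope of the difference, with a free intercept, is 0.0338 per 8 weeks. If T falls linearly to half by week 40, the slope is −T/6 per 8 weeks; T = 0.10 gives Φ(−0.0167/0.0338 − 1.645) = 0.02.

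Probability of a positive test with no adaptation effect:

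| Test | T = 0.05 | T = 0.10 | T = 0.20 |
|---|---|---|---|
| Level, week 16 | 0.17 | 0.41 | 0.88 |
| Level, week 40 (n = 343) | 0.16 | 0.37 | 0.84 |
| Level, week 40 (n = 309.5) | 0.15 | 0.34 | 0.80 |
| Average of four visits | 0.29 | 0.71 | 0.997 |
| Slope, constant T | 0.05 | 0.05 | 0.05 |
| Slope, T halving by week 40 | 0.03 | 0.02 | 0.004 |

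Level comparisons are exposed. A pure slope test is not exposed to a carry-over that is constant or fading, though it would be to one that grows.

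**The case against.** The strongest reply is that nothing is wrong with the comparison. The Research Description and Condition Assignment sections disclose the combined design, Hypothesis 3a is worded simply as DDD against SSD, and both labels were defined as covering triage and adaptation. On that view one aim sentence is narrower than its own hypothesis, and the matter is a clarification. This stands as far as it goes: the randomised contrast is sound. But the aim sentence frames the reported conclusion, and it conflicts with the sections that disclose the design. A statistical analysis plan cannot repair that, because no model can separate components that were assigned together.

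Second, the probabilities need an assumed carry-over and an assumed test. The power statement speaks of a linearly growing difference, and a slope test of that kind would be protected against a constant carry-over. This also stands: the figures illustrate and do not measure a defect. The power statement does not fix the Aim 3 test, however, and Hypothesis 3a is stated visit by visit. The identification problem does not depend on the figures.

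Third, week 16 is a legitimate comparison of strategies. Earlier decisions are an intended feature of the DDD approach (Specific Aim 2 analysis), and suicidality can prompt a move in either arm before then. Agreed; week 16 needs a statement of what it compares, not removal.

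Fourth, the later decision counts assume that enrolment year fixes review frequency, which the protocol does not say. This affects only the later rows of that table.

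**Conclusion.** The point holds, with high confidence on the design logic. The Aim 3 sentence claims an effect of adaptation alone, which this design cannot isolate. The SSD v DDD contrast at weeks 16 to 40 estimates the combined DDD strategy: triage plus adaptation at its own frequency. At week 16 it sets DDD triage plus early DDD adaptation against SSD before any scheduled SSD move.

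The size of any misattribution is unknown, because it depends on the persisting triage effect and on the test. With level tests and an assumed carry-over of 0.05 to 0.20 SD, the chance of a positive Aim 3 result without any adaptation effect runs from about 0.15 at a single visit to 0.997 for the four-visit average. With a pure slope test it is 0.05 or less, provided the carry-over does not grow. The wording should be corrected; the comparison itself need not change.

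**What to change.** Leave the care pathways, randomisation and contrast as they are, and change the text:
- Restate Aim 3 and its conclusion as the effect of the combined DDD strategy (triage plus adaptation at its own frequency) v the SSD strategy.
- Do the same for the cost-effectiveness analysis if it uses this contrast; the protocol names no comparator for it.
- Add a note that week 16 compares DDD triage plus early DDD adaptation with SSD before any scheduled SSD adaptation.
- Do not present Year 1 v Years 2-5 as isolating adaptation.

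Two editorial items belong with this. The Aim 1 analysis calls its groups adaptation arms, although Aim 1 concerns triage. The pooled week 8 estimate may also include some early adaptation from Year 2: about 100 of 500 DDD participants, so an assumed early effect of 0.05-0.20 SD moves it by (100/500) × 0.05 to (100/500) × 0.20, or 0.01-0.04 SD. A note is enough, and Year 2 stays in the analysis.

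The cost is a few sentences, with no change to sample, contrast or power. An adaptation-only claim would instead need a separate randomisation at the adaptation stage, which rewording does not provide.
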